9.5 Withdrawal from the Study and/or Treatment

A subject will be withdrawn from the study if ANY of the following criteria are met:

1. The subject requests to voluntarily withdraw from further participation in study.
2. The subject is significantly noncompliant with the protocol.
3. A female subject becomes pregnant while on the study.
4. Continuing in the study would be detrimental to the subject's safety in the opinion of the Investigator, for example:
 - a. The subject experiences intolerable AEs, SAEs, or adverse events of special interest (AESIs).
 - b. The subject has clinically significant changes in safety parameters at any of the postdose time points, as confirmed with a repeat assessment performed as soon as possible after the initial out-of-range result.
 - c. The subject experiences any clinically significant adverse findings from postbaseline nevi (Melanocytic Lesions) evaluation and adverse change is demonstrated histologically and confirmed by central pathologist. Visual evaluation of change will not be acceptable criteria for permanent discharge from treatment (Section 12.4).
 - d. Development of any clinically significant liver abnormalities defined as follows:

- ALT or AST $> 8 \times$ ULN.
- ALT or AST $> 5 \times$ ULN for more than 2 weeks.
- Elevated total bilirubin $> 2 \times$ ULN and ALT or AST $> 3 \times$ ULN or
- Symptoms consistent with liver dysfunction (e.g., fatigue, nausea, vomiting, abdominal pain or tenderness, fever, rash, eosinophilia $> 5\%$) with concomitant ALT or AST values $> 3 \times$ ULN.

Subjects meeting the laboratory criteria of ALT/AST and total bilirubin defined above (with or without alternative etiology), regardless of whether clinically significant or not, should be reported as a hepatic AESI (Section 14.3). The Investigator should discuss with the Sponsor Medical Monitor about the determination of etiology and the potential of interruption or withdrawal from study drug.

In the case of an increase of ALT or AST $> 3 \times$ ULN, it is preferable to be followed by repeat testing within 48 to 72 hours of at least four of the usual serum measures (ALT, AST, ALP, and total bilirubin) at local or central laboratory to confirm the abnormalities and to determine if they are increasing or decreasing. In addition, repeat laboratory testing can include albumin, CK, direct and indirect bilirubin, GGT, and PT/INR. There also should be inquiry made about symptoms. A detailed history including but not limited to the following formations, such as symptoms, prior or concurrent disease, concomitant drugs (including nonprescription medications, herbal and dietary supplement preparations), alcohol use, recreational drug use, exposure to environmental chemical agents, should be collected. Further testing for acute hepatitis A, B, C, D, and E infection, autoimmune biomarkers and liver imaging (e.g., biliary tract) may be warranted.

Any other laboratory or clinical abnormality that the Sponsor Medical Monitor and/or Investigator considered as clinically significant should be considered as a potential reason for interruption (see Section 10.1.3.3) or withdrawal from study drug. Subjects who have withdrawn from study drug may remain in the study and be followed per protocol (Section 14.6). In addition, a subject may be withdrawn from study drug at any time for reason(s) other than those listed here. Subjects who have withdrawn from study drug cannot resume study drug.

Subjects who prematurely discontinue study treatment (withdraw from study drug) before the EOT should be encouraged to remain in the study and complete all the required study assessments and procedures through Week 52 based on the Investigator's discretion.

If a subject decides to permanently withdraw consent from the study, every attempt should be made to have the subject complete the ET visit and perform the assessments listed at Week 52 for the collection and source documentation of safety information such as AEs, dosing compliance, and review concomitant medications and date of last dose of study drug. Return of unused medication will be performed by courier where allowed.

PK blood samples are not required for subjects who have withdrawn from study drug and their last dose is ≥ 7 days before the next time point of a PK blood sample collection.

If a subject is discontinued prematurely from either study treatment or permanently from the study, the date and the reason of the subject's discontinuation will be recorded on the site source documents and in the electronic Case Report Form (eCRF).

In the event a subject does not return to the clinical site for the ET and/or safety follow-up visit, the Investigator must make every effort to contact the subject by telephone to discuss AEs, dosing compliance, and review concomitant medications. In these cases, the collected information (AEs, concomitant medications, date of last dose of medication, etc.) via telephone will be documented in the site source documents and eCRF. Return of unused study drug and any other materials will be performed by courier where allowed.

Unresolved AEs/SAEs will be followed according to Section 14.9.

Subjects who become pregnant during the study should be withdrawn from the study treatment. Also see Section 14.10 for necessary documentation and procedures for following up with the subject.

Subjects withdrawn from the study following randomization into the double-blind treatment period and prior to dosing may not re-enter the study.

9.6 Study-Stopping Criteria

The study may be terminated by the Sponsor at any time upon becoming aware of data that could compromise the safety and/or well-being of subjects, or for any other reason it deems appropriate.

10 STUDY PLAN

10.1 Description of Study Periods

Refer to (Table 1) for an outline of procedures required at each study period and/or visit.

Prior to performing any study procedures, the Investigator (or designated personnel) will ensure that the subject is provided full and adequate oral and written information about the study and the subject must sign the Informed Consent Form (ICF), as described in Section 17.2.1.

10.1.1 Screening Period

Screening assessments will be performed up to 28 days prior to Day 1 of the double-blind treatment period. All screening evaluations must be completed and reviewed to confirm that potential subjects meet all eligibility criteria.

10.1.2 Rescreening

At the end of the screening period, if a subject has not met all eligibility criteria at the end of the screening period, the subject will be registered as a screen failure. Screen failures may be eligible for rescreening 1-time following consultation with the Sponsor and Medical Monitor.

Note: If the rescreening occurs more than 30 days after the first screening and signing of the original ICF, all screening procedures, including ICF, must be repeated. If within 30 days, repeat assessments should be discussed with the Medical Monitor.

If a subject does not meet eligibility criteria for laboratory and pulmonary function tests (PFTs), the subject may undergo repeat laboratory and PFTs up to 2 additional times during the 4-week screening period. Repeat of laboratory or PFTs is not considered rescreening.

10.1.3 Double-blind Treatment Period

Subjects who successfully complete the screening period will return to the clinical site on Day 1 of the double-blind treatment period to reconfirm his/her eligibility by reviewing the inclusion and exclusion criteria (Table 1) and evaluate other baseline criteria prior to randomization. To be randomized into the double-blind treatment period, the subject must meet the required criteria at screening and at baseline. Eligible subjects will be randomized, and study drug administration will begin on Day 1 (Visit 2) after confirmation of all baseline criteria.

Study visits will occur at the study site per the Schedule of Activities (Table 1).

10.1.3.1 Dose Reduction Visit

If a subject experience any intolerable AEs, the dose can be reduced as described below in Section 10.1.3.2. Subjects with intolerable AEs, will have to come back to the clinical site for an unscheduled visit where the following procedures will be performed:

- Physical examination including vital signs.
- Adverse events and concomitant medications, if any, will be assessed since from the previous visit.
- Local urine pregnancy test (if applicable).
- Safety blood and urine samples will be collected and submitted to the central laboratory for analysis.

- Study drug will be collected, IWRS will allocate new study drug, and treatment compliance will be reviewed.

If a dose reduction is deemed necessary by the Principal Investigator, the IWRS will be used for assignment of the new blister packs to be provided to the subject for dose reduction and study drug dispensation. The date of dose reduction visit and the reason will be recorded in the eCRF.

10.1.3.2 Dose Reduction Criteria

Subjects will be informed regarding potential side effects. If the side effects experienced by subjects are not manageable through nonpharmacologic and pharmacologic treatment (using standard of care), dose reduction (from 300 mg QD to 200 mg QD, or from 200 mg QD to 100 mg QD) should be considered to manage the incidence and/or intensity of the subject-reported AEs (including but not limited to vomiting, diarrhea, headache, hyperpigmentation).

For safety reasons, the Investigator may also decide to implement a dose reduction for a subject. The following are criteria for Investigator initiated dose reduction:

- AEs which are classified as serious and/or moderate/severe (in severity), which did not improve with clinical management according to standard of care per Investigator's judgement, AND
- AEs assessed as having reasonable possibility of relationship to MT-7117 per Investigator's judgement (Section 14.5).

Examples of severe AEs include AE which limit self-care activities of daily living (independently eat, dress, walk/transfer from 1 position to another, bathe, toilet, maintaining bowel/bladder continence).

Note: Dose up-titration after dose reduction is not allowed.

10.1.3.3 Dose Interruption

Dose interruption can be considered after the discussion with the Sponsor Medical Monitor in the case, such as

- 1) in subjects with suspicious lesions or change in nevi (Melanocytic Lesions) that had their dose temporarily interrupted can resume study treatment at the same dose they were interrupted at after the evaluations are complete and nevi (Melanocytic Lesions) and/or other lesions are determined to be benign; or
- 2) in a subject with an initial positive urine pregnancy test, awaiting a confirmatory test. If the confirmatory test is definitively negative, dosing may resume at the same dose they were interrupted; or
- 3) in a subject with any laboratory or clinical abnormality such as meeting the criteria of AESI (see Section 14.3 and 14.3.1), awaiting a confirmatory test and/or a judgement whether it is clinically significant. Resumption of dosing at the same dose they were interrupted will be considered based on the discussion with the Sponsor Medical Monitor and Investigator and should be closely followed up.

At any time during the study, subjects may be withdrawn from study treatment if continuing study treatment would be detrimental to the subject's safety in the opinion of the Investigator.

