12.7 Pregnancy Test

Pregnancy test is to be performed at all visits for female subjects of child-bearing potential. A serum pregnancy test will be performed at Visit 1, a urine pregnancy test (on-site) will be performed at all other site visits, and a urine dipstick pregnancy test will be performed at Telephone Visit 6A and 7A (Table 1).

- A serum pregnancy test on site: Visit 1 (Screening visit)
- A urine pregnancy test on site: Visit 2, 3, 4, 5, 6, 7 and 8 (Day 1, Week 2, 6, 16, 26, 39, and 52) and follow-up visit (Week 56)
- A urine dipstick pregnancy test: Telephone Visit 6A and 7A (Week 32 and 45)

Subject will have Telephone Visits (Visits 6A and 7A, Week 32 and 45, respectively), and a urine dipstick pregnancy test at home or other home testing arrangements will be performed.

The result of every urine dipstick pregnancy test should be actively requested by the site at Telephone Visits as soon as the test is due. The subject must report the result to the site without delay.

A urine dipstick pregnancy test may also be performed using alternatives such as that the subject may come to the clinic or go to a local laboratory for administration of the test. Such arrangements must be approved by the Sponsor.

If the result of the pregnancy test is positive via urine test, it must be confirmed with a serum pregnancy test, and the dose should be temporarily interrupted until it is confirmed that subject is not pregnant. In the event of a pregnancy, a referral to an obstetrician/gynecologist for confirmation of pregnancy must be organized as soon as possible. In addition, the pregnancy must be reported to the Sponsor as described in Section 14.10. In the event that a pregnancy test result is uncertain, the patient should contact the site immediately to discuss further steps (e.g., exclusion of pregnancy by serum pregnancy test).

The study treatment can be resumed at the same dose prior to the interruption if confirmatory test is definitely negative.

Importantly, any subject who becomes pregnant while on the study treatment must be withdrawn from the treatment.

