14.3.1 Management and Evaluation of Hepatic Adverse Events of Special Interest

Hepatic AESIs should be treated per the Investigator's approved standard of care and assessed for possible alternative etiology(ies). Hepatic AESIs will be followed clinically until resolution.

Subjects meeting the laboratory criteria of ALT/AST and total bilirubin defined in Section 14.3 (with or without alternative etiology), regardless of whether clinically significant or not, should be reported as a hepatic AE of special interest (AESI).

In the case of an increase of ALT or AST $> 3 \times$ ULN, it is preferable to be followed by repeat testing within 48 to 72 hours of at least four of the usual serum measures (ALT, AST, ALP, and total bilirubin) at local or central laboratory to confirm the abnormalities and to determine if they are increasing or decreasing. In addition, repeat laboratory testing can include albumin, CK, direct and indirect bilirubin, GGT, and PT/INR. There also should be inquiry made about symptoms. A detailed history including but not limited to the following formations, such as symptoms, prior or concurrent disease, concomitant drugs (including nonprescription medications, herbal and dietary supplement preparations), alcohol use, recreational drug use, exposure to environmental chemical agents, should be collected. Further testing for acute hepatitis A, B, C, D, and E infection, autoimmune biomarkers and liver imaging (e.g., biliary tract) may be warranted.

Regarding any subject who meets the AESI criteria, the Investigator should discuss with the Sponsor Medical Monitor about the determination of etiology and the possibility for

interruption (see Section 10.1.3.3) or withdrawal from study drug. Resumption of dosing will be considered based on the discussion with the Sponsor Medical Monitor and Investigator and should be closely followed up.

14.4 All hepatic AESIs (including event management and evaluation) will be recorded and reported similar to SAEs as described in Section 14.8. Severity of Adverse Events

The severity of AEs will be classified according to the following criteria:

- Mild: The event is transient and easily tolerated by the subject.
- Moderate: The event causes discomfort and interferes with the subject's general condition.
- Severe: The event causes considerable interference with the subject's general condition and may be incapacitating.

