If it is necessary to amend the Protocol during the study, proper notification will be made to the regulatory authorities and IRB/IECs in the form of a Protocol Modification. Protocol Modification requiring IRB/IEC approval may be implemented only after a copy of the IRB/IEC's approval/favorable opinion letter has been transmitted to the Sponsor and regulatory

authority approval has been obtained (if required). Protocol Modifications that are intended to eliminate an apparent immediate hazard to subjects may be implemented prior to receiving Sponsor, regulatory authority and/or IRB/IEC approval. However, in this case, approval must be obtained as soon as possible after implementation.

Any Protocol or other deviations that occur during the study will be documented and reported to the Sponsor. Depending on the nature of the deviation, this may be reported to the appropriate regulatory authority and IRB/IEC.

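### Protocol 10.1.3.3 makes interruption of study drug optional, after a Medical Monitor discussion, for a positive urine pregnancy test (item 2) and suspicious nevi (item 1), whereas 12.7 and 12.4 direct it.

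*Protocol*

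**What the plan says.** Protocol 10.1.3.3 (Dose Interruption) has one lead-in for three cases: "Dose interruption can be considered after the discussion with the Sponsor Medical Monitor in the case, such as". Item 1 concerns suspicious lesions or changing nevi. Item 2 is "in a subject with an initial positive urine pregnancy test, awaiting a confirmatory test". Item 3 concerns laboratory or clinical abnormalities, including those that meet the criteria for an adverse event of special interest (AESI).

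Protocol 12.7 (Pregnancy Test) says of a positive urine result that "it must be confirmed with a serum pregnancy test" and that "the dose should be temporarily interrupted until it is confirmed that subject is not pregnant". It does not make the interruption depend on contacting the Medical Monitor.

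Protocol 12.4 (Nevi Evaluation) says that a subject with suspicious nevi of clinical concern will be taken off treatment temporarily and referred for evaluation. It does not ask for a discussion first either.

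SAP 3.2.4 repeats the 10.1.3.3 wording as background.

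**The concern.** Two sections of one protocol give different instructions for the same subject at the same moment. One leaves interruption to judgement after a conversation with the sponsor; the other tells the site to interrupt. An investigator who opens 10.1.3.3, the section headed for this purpose, is not told to stop the drug and is not referred to 12.7 or 12.4.

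What is at stake is avoidable dosing while a pregnancy or a suspicious pigmented lesion is being clarified. The protocol treats both as real risks. Section 8.2.1.1 reports fetal skeletal anomalies in mice at 500 mg/kg/day (a dose lethal to adult females) and litter loss in rats at 300 mg/kg/day, and requires contraception. Section 12.4 provides for biopsy and central pathology review. Timing matters most for the home dipstick tests at Weeks 32 and 45, when the subject is off site and serum confirmation still has to be arranged.

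**Working it through.** No sample size, error rate or event figure is involved, so the check is a comparison of texts.

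**Step 1. Set the rules side by side.**

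| Question | Positive urine test: 10.1.3.3 item 2 | Positive urine test: 12.7 | Suspicious nevi: 10.1.3.3 item 1 | Suspicious nevi: 12.4 |
|---|---|---|---|---|
| Is the drug stopped? | Can be considered | Should be | Can be considered | Will be |
| Medical Monitor discussion first? | Yes | Not required | Yes | Not required |
| When may dosing resume? | Confirmatory test negative | Confirmatory test negative | Lesion benign | Benign and not clinically significant on central assessment |
| At what dose? | Same | Same | Same | Same |

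The resumption rules essentially agree; 12.4 is slightly fuller. The rules on whether and when to stop do not agree.

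**Step 2. Look for text that reconciles them.** Sections 9.5 and 14.10 deal with a subject who has become pregnant, not one awaiting confirmation. The closing sentence of 10.1.3.3 is about withdrawal and is itself permissive. Items 1 and 2 do not cite 12.4 or 12.7, those sections do not cite 10.1.3.3, and no readable text says which prevails.

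**Step 3. Check item 3.** For laboratory and clinical abnormalities, 9.5 says they "should be considered as a potential reason for interruption (see Section 10.1.3.3) or withdrawal from study drug". For hepatic AESIs, 14.3.1 also makes interruption a matter for discussion with the Medical Monitor. The permissive lead-in therefore matches the rest of the protocol for item 3, and only items 1 and 2 are out of line.

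**Step 4. See how often the pregnancy rule could be called on.** Section 12.7 schedules urine tests during continuing treatment at Weeks 2, 6, 16, 26 and 39 on site and at Weeks 32 and 45 at home: 5 + 2 = 7 per woman of child-bearing potential. Day 1 (predose), Week 52 (end of treatment) and Week 56 (follow-up) are left out. This counts occasions and does not measure harm. The documents give no positive-test rate, no time limit for the Medical Monitor discussion and no time limit for the serum result, so no figure for extra exposure can be computed.

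**The case against.** The strongest reply is that the operative rules are already in the protocol. Sections 12.7 and 12.4 are the dedicated sections, and a specific rule is ordinarily read as governing over an illustrative list. Items 1 and 2 both set resumption terms that presuppose an interruption. A site that stops the drug and then calls the Medical Monitor complies with everything. All of this stands, and it is why the point is minor. It does not make 10.1.3.3 say that interruption is required or immediate.

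Four stronger readings are tempting, and the documents do not support them:

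- *The protocol tells sites to keep dosing.* It does not. Section 10.1.3.3 never instructs continuation, and 9.5, 12.7 and 14.10 all require treatment to be withdrawn once pregnancy is established.
- *A positive test at a dose-reduction visit escapes 12.7.* Section 10.1.3.1 calls for a urine test at that visit and 12.7's list does not name it. But 12.7's interruption rule is triggered by a positive urine result, not by membership of the list, so that test is covered. Nor do the two permitted dose reductions cap the number of such tests, because the test is done when the subject returns with intolerable events, before any reduction is decided.
- *The protocol's cross-references steer pregnancy cases to the weaker rule.* Sections 9.5 and 14.3.1 do refer to 10.1.3.3, but for laboratory or clinical abnormalities and hepatic AESIs. On pregnancy, 9.5 refers to 14.10.
- *Section 12.7 makes interruption mandatory.* It says *should* for the interruption and *must* only for the serum confirmation. It is a direction, clearly stronger than 10.1.3.3, but not an absolute one.

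**Conclusion.** The inconsistency is real and rests on the wording alone. Items 1 and 2 of 10.1.3.3 place under an optional, discussion-first lead-in two situations in which 12.4 and 12.7 direct interruption without that step. A site using 10.1.3.3 alone could delay or omit an interruption that the protocol elsewhere calls for.

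The size is small. Few positive pregnancy tests are expected, because Appendix 3 requires women of child-bearing potential to use a highly effective method together with a male barrier. Sites that know 12.7 and 12.4 will act correctly. A reader might infer a measurable excess of fetal exposure, or a consequence for the analysis. Neither follows: the exposure cannot be derived, and no endpoint, population or analysis depends on this text. The conclusion assumes that no redacted passage reconciles the sections. It merits correction as a safety clarification, without urgency.

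**What to change.** Take items 1 and 2 out from under the lead-in of 10.1.3.3 and replace them with text along these lines:

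- *For suspicious nevi of clinical concern, study drug is interrupted per Section 12.4; for any positive urine pregnancy test (site, home or unscheduled), study drug is interrupted per Section 12.7. In neither case does the site wait for the Medical Monitor discussion; the Medical Monitor is informed.*
- *Dosing may resume at the same dose only after a benign, not clinically significant finding, or after a definitively negative confirmatory serum test, respectively.*

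Add references back to 10.1.3.3 in 12.4 and 12.7. Leave item 3 under the existing lead-in. Matching the background text in SAP 3.2.4 is optional, since it defines no analysis.

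The cost is a few sentences. Section 17.2.2 says "Protocol Modification requiring IRB/IEC approval may be implemented only after" that approval is in hand, so the change is best carried in the next amendment. The only step that 12.4 and 12.7 do not already contain is informing the Medical Monitor, which preserves the contact that 10.1.3.3 asks for. The drawback is an occasional short interruption for a false-positive test or a benign lesion, which 12.7 and 12.4 already accept. No statistical output changes.
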